4. ANALYSIS POPULATIONS

Population	Definition / Criteria	Analyses Evaluated
Safety	
 • All randomized subjects who received at least one dose of blinded study medication. • Subjects will be analysed according to the treatment a subject actually received. 	
 • Primary population for all safety analyses and data presentations
Microbiologic-Intent-To-Treat (mITT)	
 • All randomized subjects who receive at least one dose of blinded study medication and have microscopically-confirmed vivax parasitemia at Baseline. • Subjects will be analysed according to the treatment a subject was randomized to. 	
 • Primary population for all efficacy analyses
Per-Protocol (PP)	
 • All subjects in the mITT population for whom there were no major protocol violations. 	
 • Sensitivity/ supporting analyses of efficacy data only
Ophthalmic Safety	
 • All subjects in the safety population who have results from any eye assessments. 	
 • Analyses of ophthalmic endpoints

NOTES :

- Please refer to [Appendix 14](#): List of Data Displays which details the population to be used for each displays being generated.
- PK and PK/PD data are being handled outside of this RAP so PK and PK/PD populations are not included in this table.

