8.1.2. Planned Efficacy Statistical Analyses

Secondary Statistical Analyses
Endpoint(s)

 Relapse-free efficacy six months post-dosing Relapse-free efficacy four months post-dosing See Section 13.6.4 for derivations including censoring.
Model Specification

 Estimates for the relapse-free efficacy rate and time to relapse will be determined for each treatment group using the Kaplan-Meier method. Cox Proportional Hazards model with region and treatment as covariates will provide the hazard ratio mITT population

Secondary Statistical Analyses
Model Checking & Diagnostics

 Refer to Appendix 12: Model Checking and Diagnostics for Statistical Analyses.
Model Results Presentation

 Summary of the proportion of subjects with relapse-free efficacy by treatment group as n (%), including the sub-reasons for why subjects are not considered relapse-free defined in Section 13.6.4 (Table 2.5 for 6 months, Table 2.7 for 4 months). Note only the sub-reasons that apply to the population being displayed will be included. Analysis tables (Table 2.9 for 6 months, Table 2.11 for 4 months) will show: 
 Number of subjects with an observed relapse and numbers of subjects censored (censored prior to 6/4 months, and censored relapse-free at 6/4 months) Kaplan-Meier estimate and 95% confidence intervals of the relapse-free efficacy rate at 6/4 months for each treatment Kaplan-Meier quartile estimates and 95% confidence intervals of time to relapse Hazard ratio of TQ+CQ vs PQ+CQ over the first 6/4 months from Cox Proportional Hazards model 95% CI Kaplan-Meier survival curves will also be produced for 6 months (Figure 2.1).

Sensitivity and Supportive Statistical Analyses
1. Per Protocol population – Relapse free efficacy at 6 months and 4 months

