
 Summary of the proportion of subjects with relapse-free efficacy by treatment group as n (%), including the sub-reasons for why subjects are not considered relapse-free defined in Section 13.6.4 (Table 2.6 for 6 months, Table 2.8 for 4 months). Note only the sub-reasons that apply to the population being displayed will be included. Analysis tables (Table 2.10 for 6 months, Table 2.12 for 4 months) will show: 
 Number of subjects with an observed relapse and numbers of subjects censored (censored prior to 6/4 months, and censored relapse-free at 6 months) Kaplan-Meier estimate and 95% confidence intervals of the relapse-free efficacy rate at 6/4 months for each treatment Kaplan-Meier quartile estimates and 95% confidence intervals of time to relapse Hazard ratio of TQ+CQ vs PQ+CQ over the first 6/4 months from Cox Proportional Hazards model 95% CI Kaplan-Meier survival curves will also be produced for 6 months (Figure 2.2).
2. Logistic Regression Model – 6 months and 4 months

 6 months: Table 2.13, 4 months: Table 2.14 Logistic regression model with region and treatment as covariates. Response variable = relapse free (confirmed at 6 (or 4) months) vs relapse (confirmed relapse at or prior to 6 (or 4) months). Subjects who are censored prior to 6 (or 4) months will be excluded from the analysis. mITT only Present the number and percentage of subjects considered relapse free, the adjusted odds ratio of TQ+CQ vs PQ+CQ and 95% CI for the odds ratio
3. Missing=Failure analysis - 6 months and 4 months

 See Section 13.6.4 for derivation of missing=failure dataset Logistic regression with region and treatment as covariates

Sensitivity and Supportive Statistical Analyses

 • mITT only • Presentation of results (6 months: Table 2.15, 4 months: Table 2.16): 
 • Number and percentage of subjects considered relapse free • Adjusted odds ratio of TQ+CQ vs PQ+CQ and 95% CI
4. Missing on or after Day 29 = Failure analysis – 6 months

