13.1. Appendix 1: Protocol Deviation Management and Definitions for Per Protocol Population

13.1.1. Protocol deviations

Major protocol violations could impact the ability to assess efficacy and our primary endpoints for our study. A subject meeting any of the following criteria will be excluded from the Per Protocol population:

Number	Exclusion Description
1	Subject does not have a parasitology assessment within window for any of the Day 2, Day 3, Day 29, Day 60, Day 90, Day 120, Day 150 or Day 180 visits
2	Subject does not demonstrate initial parasite clearance but does not receive rescue medication
3	When in the clinic on Day 1 to 3, subject vomited a dose of study medication and either vomited the redose, or a redose was not given
4	PQ/PQ placebo pill count suggests that the subject failed to take two or more scheduled doses when away from the clinic
5	Violation of any of the following entry criteria: 
 • Subject had a mixed malaria infection at baseline • Subject had an asexual P. vivax parasite count ≤ 100 or ≥ 100000 • Subject had a severe malaria infection • Subject had severe vomiting or diarrhoea • Subject had taken anti-malarials within the previous 30 days
6	The subject has taken/received: 
 • anti-malarials (e.g., artemisinin-based combination therapies, mefloquine, primaquine, or any other 4- or 8-aminoquinoline) within 30 days prior to study entry. • treatment with any investigational drug within 30 days of study entry, or within 5 half-lives, whichever is longer. • a concomitant medication with an anti-malarial activity between Day 1 and the Day 180 visit, and remained parasite negative throughout the study. A list of all concomitant medications will be reviewed by a GSK clinician prior to unblinding the study, and classified accordingly

NOTES:

- A listing will be produced for the PP population showing
 1. individual subject numbers for each protocol violation
 2. the number and percentage of subjects for each violation
 3. the total number of subjects with one or more violation will be tabulated, by type of violation.

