13.7.2.3. Handling of Missing Data for Statistical Analysis

Element	Reporting Detail
Incidence of Haemolysis	
 For the primary analysis only observed data will be used. A sensitivity analysis will be performed where missing haemolysis data before Study Day 17 will be imputed as 'haemolysis=YES'.
Relapse-free efficacy and time to event endpoints	
 For all analyses of the mITT population, subjects will not be excluded from any statistical analyses. From the Day 29 assessment onwards, subjects who have not relapsed but fail to have an evaluable parasite smear within the visit window for every scheduled visit will be excluded from the PP population. See Section 13.6.4 for further details on how missing assessments will be censored.
Derived variables	
 For derived variables, details of how any missing eCRF data will be handled are provided in Section 13.6.

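### The 4-month per-protocol analysis uses a population that depends on Day 150 and Day 180 data, so confirmed 4-month successes can be removed for events after the endpoint has closed

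*Supplement*

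**What the plan says.** All references are to the RAP, Amendment 1, unless stated.

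- Section 4 defines a single PP population, tied to no endpoint: "All subjects in the mITT population for whom there were no major protocol violations". Its role is "supporting analyses of efficacy data only".
- Section 13.1.1, item 1, excludes a subject who lacks a blood smear "within window for any of the Day 2, Day 3, Day 29, Day 60, Day 90, Day 120, Day 150 or Day 180 visits". Item 6 excludes a subject who took a drug with anti-malarial activity "between Day 1 and the Day 180 visit, and remained parasite negative throughout the study".
- Section 13.7.2.3 describes the smear rule from Day 29 onwards differently: "subjects who have not relapsed but fail to have an evaluable parasite smear within the visit window for every scheduled visit will be excluded". That exclusion, too, is from the PP set.
- Section 8.1.2 applies this population to "Relapse free efficacy at 6 months and 4 months", and adds: "Analysis tables (Table 2.10 for 6 months, Table 2.12 for 4 months) will show" the Kaplan-Meier rate per arm and the hazard ratio. Section 13.14.4 lists Table 2.12 as a headline deliverable.
- Section 13.6.4 decides the 4-month outcome on the first smear in Study Days 110 to 130, and counts anti-malarial use only up to that smear.

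No 4-month version of the PP population is defined.

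**The concern.** A subject whose smears are all present and negative through the Day 120 visit is a confirmed 4-month success. Under the current rules that subject still drops out of the 4-month PP analysis for missing the Day 150 or Day 180 smear, or for taking a drug with anti-malarial activity after the 4-month smear. Neither event bears on whether the 4-month outcome was validly observed.

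If such removals fall on successes and not on relapses, the 4-month PP relapse-free rate is conditioned on what happens after the time it describes, and it is too low. If they fall on both alike, the analysis is smaller than it needs to be. Appendix 5 of the protocol counts several ordinary antibiotics and albendazole among drugs with anti-malarial activity, so the late-medication route is not confined to malaria treatment.

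**Working it through.** The plan states no sample size, power or expected rate for the 4-month PP analysis, so there is no figure of its own to reproduce. The check is a comparison of dates and rules, followed by an illustration on assumed rates.

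**Step 1: dates.** The Time and Events tolerances reproduce the windows in section 13.3.1:
- Day 120 ± 10 gives Study Days 110 to 130.
- Day 150 ± 10 gives 140 to 160.
- Day 180 - 14/+21 gives 166 to 201.

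The 4-month outcome therefore closes 140 - 130 = 10 days before the Day 150 window opens, and 166 - 130 = 36 days before the Day 180 window opens.

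**Step 2: who is removed by late events.**
- *Item 6.* Only subjects who stayed negative throughout can meet it. A 4-month relapser cannot, so the rule removes successes only.
- *Smear rule as in section 13.7.2.3.* Only subjects who have not relapsed are excluded. A 4-month relapser is kept, and so is a 4-month success who relapses later.
- *Smear rule as in item 1, read literally.* Relapsers have no exemption. If attendance is equal, successes and relapsers are thinned by the same factor (1 - m), which cancels: S(1 - m) / [S(1 - m) + (1 - S)(1 - m)] = S. Subjects are lost but the rate is not biased.

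**Step 3: size under section 13.7.2.3.** Let S be the true 4-month relapse-free rate and k the share of 4-month successes retained. The reported rate is R = Sk / (Sk + 1 - S). Assume S = 75%, with a proportion m of non-relapsers missing each of Days 150 and 180. Neither figure is in the documents. If the same subjects miss both visits, k = 1 - m. If misses are independent, k = (1 - m)².

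| m | Same subjects: k | R | Bias (points) | Independent: k | R | Bias (points) |
|---|---|---|---|---|---|---|
| 3% | 0.97 | 74.4% | -0.6 | 0.9409 | 73.8% | -1.2 |
| 5% | 0.95 | 74.0% | -1.0 | 0.9025 | 73.0% | -2.0 |
| 10% | 0.90 | 73.0% | -2.0 | 0.81 | 70.8% | -4.2 |

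For example, m = 5% with full overlap gives 0.7125 / (0.7125 + 0.25) = 74.0%. The table lets every 4-month success be deleted. Late relapsers are in fact kept, and unscheduled or withdrawal smears can fill an empty window (section 13.3.1), so both columns lean towards the larger side.

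**Step 4: the treatment comparison.** Take the hazard ratio as a ratio of log survival, with independent misses equal in both arms.
- Assumed true rates of 75% and 65% give ln 0.75 / ln 0.65 = 0.668.
- With m = 5% this becomes 0.672, and with m = 10% it becomes 0.676.

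For unequal loss, assume S = 80% in both arms, 5% relapsing after Day 130, and total late loss of 5% on TQ against 15% on PQ. The deleted shares are 0.80 × 0.95 × 0.05 = 0.038 and 0.80 × 0.95 × 0.15 = 0.114. The reported rates are 0.762 / 0.962 = 79.2% and 0.686 / 0.886 = 77.4%, a spurious difference of about 1.8 points (hazard ratio about 0.91).

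**The case against.** The strongest reply has four parts.

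- **The direction of bias rests on one of two conflicting texts.** Item 1 does not exempt relapsers, and the Time and Events footnote keeps relapsers on all scheduled visits through Day 180, so the literal rule can be applied to them. This stands for the smear rule. It does not rescue item 6, which is one-sided by its own wording.
- **The consequence is limited.** PP is supportive, no hypotheses are tested, and 4-month efficacy is secondary. The mITT 4-month tables (2.11, 2.14 and 2.16) are also headline deliverables and do not use the flag. All of this stands, and it sets the priority of the point.
- **A single PP set is defensible.** It means adherence to the whole protocol and keeps one denominator for both horizons. That is coherent as a convention. But the RAP does fit smear timing to the horizon elsewhere: the 4-month missing=failure rule in section 13.6.4 asks only for a smear in Study Days 110 to 130.
- **Differential late missingness is speculative.** The trial is double-blind and double-dummy and dosing ends by Day 15. This stands: the documents give no reason to expect it.

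A reader might infer that the TQ versus PQ comparison is distorted, or that the non-inferiority meta-analysis inherits the fault because its primary population is PP. The documents support neither. The hazard ratio barely moves under equal loss, and the Meta-Analysis Plan uses only the six-month endpoint, for which the present flag was built.

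**Conclusion.** The mismatch is real. The 4-month PP population is selected partly on smears and medication after the 4-month outcome has closed. Selection against successes is certain through item 6 and, if section 13.7.2.3 governs, through the smear rule as well; the per-arm 4-month PP rate is then biased downward. If item 1 is applied literally to everyone with equal attendance, its main effect is lost subjects.

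The size cannot be derived from the documents. On an assumed true rate of 75% and 3% to 10% missing each late visit, the bias is about -0.6 to -2.0 points when the same subjects miss both visits. The range of -1.2 to -4.2 points needs the two misses to be independent and should be read as the upper end, reduced further where unscheduled smears fill the windows. Quoting that upper range as the expected bias would go beyond the evidence, because a subject who withdraws after Day 120 misses both visits.

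The change is worth making because it is cheap and Table 2.12 is a headline output. It does not threaten the trial's main conclusions.

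**What to change.** Derive a separate 4-month PP flag. Limit item 1 to visits through Day 120, and limit the concomitant anti-malarial clause of item 6 to use up to the Day 120 smear (Study Day 130 at the latest). Use this flag for Tables 2.8 and 2.12, and keep the present flag for 6 months.

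Separately, reconcile item 1 of section 13.1.1 with section 13.7.2.3 by stating in both places whether subjects who have relapsed are exempt from the smear requirement.

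The cost is one more population flag built from data already collected, a sentence or two in the RAP before unblinding, and a footnote explaining that the 4- and 6-month PP denominators differ.

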13.2. Appendix 2: Time & Events

13.2.1. Protocol Defined Time & Events

Protocol Activity	Visit Day															
	Screening/Treatment Period ^a							Follow-Up Period							Relapse Visit ^b	Withdrawal Visit ^c
	Day 1 ^d	Day 2	Day 3	Day 5 +1d	Day 8 -/+1d	Day 11 -/+1d	Day 15 -/+2d	Day 22 -/+3d	Day 29 -/+3d	Day 60 -/+7d	Day 90 -/+7d	Day 120 -/+10d	Day 150 -/+10d	Day 180 -14/+21d	Relapse	Withdrawal
Window																
Informed Consent Process	X															
Demographic Information	X															
Initial History Only ^e	X															
Physician Assess. Malaria Signs & Symptoms	X															
Inclusion/Exclusion Criteria	X															
Efficacy Assessments																
Parasitological Assessment (blood smear)	X ^f	X ^f	X ^f		X		X	X	X	X	X	X	X	X	X	X
Plasmodium PCR Genotyping	X														X	
Plasmodium whole genome sequencing	X														X	
Safety Assessments																
Review Concomitant Medications	X	X	X	X	X	X	X	X	X	X	X	X	X	X	X	X
Vital Signs ^g	X	X	X		X	X	X	X	X	X	X	X	X	X	X	X

Protocol Activity	Visit Day															Relapse Visit ^b	Withdrawal Visit ^c
	Screening/Treatment Period ^a							Follow-Up Period									
	Day 1 ^d	Day 2	Day 3	Day 5 +1d	Day 8 -/+1d	Day 11 -/+1d	Day 15 -/+2d	Day 22 -/+3d	Day 29 -/+3d	Day 60 -/+7d	Day 90 -/+7d	Day 120 -/+10d	Day 150 -/+10d	Day 180 -14/+21d	Relapse	Withdrawal	
Window																	
Physical Examination	X	X	X		X		X	X	X	X	X	X	X	X	X	X	
ECG w/ Interpret. & Report ^h	X	X							X						X	X	
Adverse Events Assessment ⁱ	X	X	X	X	X	X	X	X	X	X	X	X	X	X	X	X	
Serious Adverse Events ⁱ	X	X	X	X	X	X	X	X	X	X	X	X	X	X	X	X	
G6PD (phenotyping) ^k	X									X		X					
G6PD and CYP2D6 (genotyping)		X															
Ophthalmological Exam (qualified sites only)	X								X		X			X ^l		X	
Laboratory Assessments																	
Hematology ^m	X		X ⁿ	X	X	X	X	X	X	X	X	X	X		X	X	
Clinical Chemistry ^o	X		X ⁿ	X	X	X	X	X	X	X	X	X			X	X	
Methemoglobin	X	X	X	X	X	X	X	X	X	X		X		X	X		
Urinalysis ^p	X		X	X	X	X	X	X	X	X	X	X		X	X		
Blood Draw for PGx		X ^q															
Pregnancy Test ^r	X						X		X	X				X	X	X	
Health Outcomes																	
Health Outcomes Assessments ^s	X						X	X ^t	X ^t	X ^t	X ^t	X ^t	X ^t	X ^t	X ^t	X ^t	

Protocol Activity	Visit Day															
	Screening/Treatment Period ^a							Follow-Up Period							Relapse Visit ^b	Withdrawal Visit ^c
	Day 1 ^d	Day 2	Day 3	Day 5	Day 8	Day 11	Day 15	Day 22	Day 29	Day 60	Day 90	Day 120	Day 150	Day 180	Relapse	Withdrawal
Window				+1d	-/+1d	-/+1d	-/+2d	-/+3d	-/+3d	-/+7d	-/+7d	-/+10d	-/+10d	-14/+21d		
Pharmacokinetic Assessments																
PK/PD Sampling ^e		X	X		X		X		X	X					X	
Investigational Product																
Dispense Open Label Chloroquine	X	X	X													
Dispense Blinded Study Medication	X ^f	X ^f														
Treatment Compliance Int. - Invest.	X	X	X	X	X	X	X									
IVRS Registration	X															

- a All subjects must remain hospitalized for Days 1 through 3.
- b Subjects who relapse will continue to be monitored for safety and efficacy at all scheduled visits through day 180. Relapse is defined by a positive blood smear with or without vivax symptoms.
- c If subjects withdraw from blinded study medication, all scheduled follow-up visits should be performed to conduct safety assessments up to and including Day 180.
- d Visit Day 1 includes all screening procedures and the first day of treatment with study medication.
- e Includes medical, disease and therapy histories.
- f Blood smears are to be taken twice a day, 6-12 hours apart for the first 3 days, or until 2 consecutive negative thick blood smears are obtained.
- g Vital signs include height and weight (screening only), blood pressure, temperature, heart rate and respiratory rate. Vital signs are to be performed twice a day on Days 1 through 3, at least 4 hours apart, and immediately prior to PK measurements.
- h ECGs are to be performed at screening (in triplicate), 12 hours after the first dose of blinded study medication, and on Day 29.
- i Adverse events are recorded from the time of the first dose of study medication.
- j Serious adverse events are recorded from the time of consent in order to fulfil international regulatory requirements.
- k G6PD phenotyping to be performed by both quantitative spectrophotometric analysis and rapid point of care test.
- l Only if Day 90 ophthalmological exam shows abnormalities.
- m Hematology includes hemoglobin, hematocrit, red blood cell/white blood cell/platelet counts, mean cell volume, white blood cell differential and reticulocyte count.

- n Hematology and clinical chemistry on Day 3 must be reviewed prior to discharge from the hospital.
- o Clinical Chemistry includes CPK, BUN, serum creatinine, total and indirect bilirubin and liver clinical chemistry.
- p Mid-stream urine will be analyzed for protein, glucose, ketones, bilirubin, blood, nitrites, urobilinogen and leukocyte esterase by dipstick method.
- q The pharmacogenetics sample must be collected at the earliest opportunity after randomization and during the in-clinic treatment visit (Days 1-3).
- r Serum or urine pregnancy test that is routinely used at site with a test sensitivity for hCG level ≤ 25 mIU/mL. FSH serum test only for post-menopausal females with less than 6 months spontaneous amenorrhea.
- s Refer to Section 6.5 of the protocol for details on health outcome data collection.
- t Health outcomes assessments will only be collected at these visits from subjects with confirmed parasitemia or from subjects with clinically relevant hemolysis.
- u Day 2 and Day 3 PK samples must be taken 6-12 hours and 24-48 hours post TQ dose.
- v Treatment with blinded study medication will begin on either Day 1 or Day 2.

13.3. Appendix 3: Assessment Windows

13.3.1. Definitions of Assessment Windows for All Analyses

Visit	Analysis Window	
	Beginning Timepoint	Ending Timepoint
Day 1	Study Day 1	Study Day 1
Day 2	Study Day 2	Study Day 2
Day 3	Study Day 3	Study Day 4
12 hours post randomised treatment ¹	11.5 hours post first dose of randomised treatment (Study Days 1-4)	12.5 hours post first dose of randomised treatment (Study Days 1-4)
Day 5	Study Day 5	Study Day 6
Day 8	Study Day 7	Study Day 9
Day 11	Study Day 10	Study Day 12
Day 15	Study Day 13	Study Day 17
Day 22	Study Day 19	Study Day 25
Day 29	Study Day 26	Study Day 32
Day 60	Study Day 53	Study Day 67
Day 90	Study Day 83	Study Day 97
Day 120	Study Day 110	Study Day 130
Day 150	Study Day 140	Study Day 160
Day 180	Study Day 166	Study Day 201

¹For ECG parameters only

For all data summarised by visit, the nominal visit description will be used. Unscheduled and withdrawal visit data will be slotted into a scheduled visit window, if no competing visit exists within the window. If there are multiple assessments within the same window which are not unscheduled visits, the earliest result will be used in the summaries.

Note that the 12 hours post dose window is used only for the ECG parameters. If there are multiple measurements within the acceptable window, the assessment closest to the nominal visit description will be used in the summaries. If triplicate readings were taken, the mean of the triplicates will be used in the summaries.

13.4. Appendix 4: Treatment States and Phases

13.4.1. Treatment Phases

Treatment phases are not required for this study.

13.4.2. Treatment States

Adverse events will be classified according to time of occurrence relative to the start of the study treatment. No other treatment states are required for this study.

